Metabolism and nutrition disorders: Hyperglycemia ^b	Hyperglycemia Grade 3(fasting plasma glucose 250 – 500mg/dL) (confirmed with a repeat fasting plasma glucose test within 48 hours) that does not resolve to grade 0 within 14 consecutive days (after initiation of oral anti-diabetic treatment)
	Hyperglycemia Grade 4
	Hyperglycemia leading to diabetic keto-acidosis, hospitalization for IV insulin infusion, or non-ketotic coma
GI disorders ^a	Diarrhea CTCAE Grade ≥ 3 for ≥ 48 hrs, despite the use of anti-diarrhea therapy
	Nausea/vomiting CTCAE Grade ≥ 3 for ≥ 48 hrs, despite the use of anti-emetic therapy
	Pancreatitis CTCAE Grade ≥ 3
Eye disorder	CTCAE Grade ≥ 3

Toxicity	DLT criteria
Blood chemistries ^c	Blood bilirubin ^d CTCAE Grade 2 for > 7 consecutive days
	Blood bilirubin ^d CTCAE Grade ≥ 3
	AST or ALT CTCAE Grade ≥ 3 in conjunction with blood bilirubin ^d CTCAE Grade ≥ 2 of any duration
	AST or ALT CTCAE Grade 3 for > 7 consecutive days
	AST or ALT CTCAE Grade 4
	Serum alkaline phosphatase CTCAE Grade 4
	Serum lipase and/or serum amylase (asymptomatic) CTCAE Grade 3 for > 7 consecutive days
	Serum lipase and/or serum amylase (asymptomatic) CTCAE Grade 4
	Serum creatinine CTCAE Grade 2 for > 7 consecutive days
	Serum creatinine CTCAE Grade ≥ 3
Other hematologic and non-hematologic toxicities	Any other clinically significant CTCAE ≥ Grade 3 toxicity
	Any intolerable CTCAE Grade 2 toxicity
	Apart from the criteria listed above, if a lower grade AE leads to a dose interruption of more than 7 consecutive days of BYL719, this AE will be considered as DLT

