9.5 Dose-Finding Phase

The dose-finding phase will follow a standard 3 + 3 design. A treatment cycle will consist of 28 days. Patients will continue on treatment until progression of disease or unacceptable toxicity.

For Arms A and B, the starting dose of BYL719 for the first cohort (Cohort 0) will be 300mg daily, which is 75% of the MTD from the phase I study. Treatment doses for BYL719 for each cohort are presented below:

Table 9-3 Dose-Finding Cohorts for Arms A and B

COHORT	BYL719 dose
+2	400mg orally once daily (100% of MTD for single agent BYL719)
+1	350mg orally once daily (87.5% of MTD for single agent BYL719)
0 (starting dose)	300mg orally once daily (75% of MTD for single agent BYL719)
-1	250mg orally once daily (62.5% of MTD for single agent BYL719)
-2	200mg orally once daily (50% of MTD for single agent BYL719)

For Arms C and D, the starting dose of BYL719 for the first cohort (Cohort 0) will be 250mg daily. Treatment doses for BYL719 for each cohort on Arms C and D are shown below:

Table 9-4 Dose-Finding Cohorts for Arms C and D

COHORT	BYL719 dose
+2	350mg
+1	300mg
0 (starting dose)	250mg
-1	200mg

During the dose-finding phase, a periodic teleconference will be held at least monthly with the primary investigator and Novartis to review toxicity data and ensure patient safety moving forward.

Dose escalation or de-escalation schema:

On each arm, three patients will be enrolled onto Cohort 0 at the starting BYL719 dose. All patients within a cohort will be observed for toxicity for one cycle (28 days) prior to entering additional patients. If a patient discontinues study participation during the first cycle (within 28 days of starting study treatment) for reasons unrelated to an adverse event, an additional patient may be enrolled to replace that subject. Between 6 and 15 patients in each arm will be necessary to determine the recommended phase II dose of BYL719 in combination with letrozole or exemestane.

There will be no inpatient dose escalation. Inpatient dose reductions of BYL719 will not be allowed during Cycle 1 (within 28 days of starting study treatment), unless a DLT has occurred and been counted towards informing enrollment of future cohorts of patients. This is in order to accurately determine the safe and tolerable dose of BYL719 when used in combination with letrozole or exemestane.

Schema for Cohort 0:

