10.10.2 Dose Reductions and Dose Delays

For patients who do not tolerate the protocol-specified dosing schedule, dose adjustments are permitted in order to allow the patient to continue the study treatment. All dose modifications should be based on the worst preceding toxicity (NCI Common Toxicity Criteria, version 4.0).

Prior to completion of Cycle 1, treatment (either BYL719 or AI or both) can be held for up to 7 days for any reason, and then resumed at the same dose. After completion of Cycle 1,

treatment (either BYL719 or AI or both) can be held for up to 3 weeks for any reason, and then resumed at the same dose. The investigator may remove any patient from study for any toxicity if he/she believes that it is in the best interest of the patient to discontinue study treatment.

Inpatient dose reductions of BYL719 will not be allowed during Cycle 1 (within 28 days of starting study treatment), unless a DLT has occurred and been counted. This is in order to accurately determine the safe and tolerable dose of BYL719 when used in combination with letrozole or exemestane.

BYL719 dose modification guidelines for toxicities considered at least possibly related to the study treatment are outlined in Table 10-2 below. If a patient experiences unacceptable toxicity that fails to resolve after a maximum BYL719 dose delay of 21 consecutive days, then the patient should be discontinued from the study treatment. In exceptional situations, if the patient is clearly benefiting from the study treatment (i.e., stable disease, partial response, complete response), and in the opinion of the investigator no safety concerns are present, the patient may remain on the study treatment. Patients who discontinue from the study for a study-related adverse event or an abnormal laboratory value must be followed as described in Section 10.10.1.

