10.10.3 Hyperglycemia Management

PI3K is a key component of the insulin signaling pathway. Therefore, hyperglycemia may be a marker of BYL719 activity on its intended target.

In the BYL719 single agent first-in-human study, hyperglycemia occurred in 24/50 patients (48%), in a dose-related fashion. At a dose of 270 mg daily, one patient experienced hyperglycemia CTCAE Grade 1, but no Grade 3/4 hyperglycemia was reported. At the MTD of 400mg daily, 10/16 (62%) of patients experienced hyperglycemia, among them 4 (25%) with Grade 3/4 hyperglycemia. In the majority of patients, hyperglycemia could be managed by administration of oral anti-diabetic drugs such as metformin or glimepiride. Occasionally treatment with insulin was required.

No hyperglycemia or related metabolic abnormalities have been noted in a large phase III studies of letrozole and exemestane.

Patients with controlled, non-insulin-dependent diabetes may be enrolled if fasting glucose <140mg/dL, even if currently requiring the use of anti-hyperglycemic agents (other than insulin). We are including these patients with well-controlled diabetes because we anticipate that they will be familiar with glucose management, and thus able to manage hyperglycemia associated with BYL719 potentially better than those patients without a prior diagnosis of diabetes.

Fasting glucose levels will be obtained at selected study visits during each cycle as shown in Table 10-1. For the purposes of dose delay decisions, glucose measurements should be in a fasted state, defined as a level obtained at least 8 hours after the most recent caloric intake.

Any patient experiencing hyperglycemia will be managed per the guidelines in the table below, and per standard medical practice for sequelae of hyperglycemia such as dehydration and acidosis.

Grade 4 hyperglycemia must be reported to the MSKCC IRB and Novartis. See Section 17.2 for reporting requirements.

Table 10.3 Hyperglycemia Management

- The below are guidelines that may be modified at the discretion of the Principal Investigator.
- Management of steroid-induced hyperglycemia and resultant decisions regarding dose-reduction are also at the discretion of the Principal Investigator.

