
Asymptomatic grade 3 (> 250 - 500 mg/dL) [> 13.9 - 27.8 mmol/L]
 
Or Grade 2 with signs or symptoms of hyperglycemia (e.g., mental status changes, excessive thirst, polyuria)
	
Omit BYL719 and re-check within 24 hours: if grade worsens or improves, follow specific recommendations. If grading is confirmed: Omit BYL719 dosing. Consider administering intravenous hydration and intervention for electrolyte/ketoacidosis/hyperosmolar disturbances as clinically appropriate Initiate or intensify medication with appropriate anti-diabetic treatment (consider adding insulin) as per investigator's discretion. Monitor fasting glucose as clinically indicated and at least twice weekly until fasting glucose resolves to ≤ Grade 1 If fasting glucose resolves to Grade 1 within 14 days, then re-start BYL719 and reduce 1 dose level If fasting glucose doesn't resolve to Grade 1 within 14 days, then discontinue patient from BYL719 Continue with anti-diabetic treatment and check fasting glucose at least weekly for 8 weeks, then continue checking at least every 2 weeks

Grade 4 (> 500 mg/dL) [\geq 27.8 mmol/L]
 
Or Grade 3 with signs or symptoms of hyperglycemia (for ex., mental status changes, excessive thirst, polyuria)
	
Omit BYL719, initiate or intensify medication with appropriate anti-diabetic treatment (consider adding insulin), re-check within 24 hours. If grade improves then follow specific grade recommendations.
 
If fasting glucoses confirmed at Grade 4: Discontinue patient from BYL719

A diabetologist consultation should always be considered.
 
Based on current experience, hyperglycemia usually resolves within a few days after BYL719 omission; temporary omission of BYL719 may be considered as clinically indicated to improve control of hyperglycemia. Special attention should be paid to the risk of hypoglycemia in patients interrupting BYL719 treatment and receiving insulin or sulfonylurea.
 
For all grades : instruct patient to follow dietary guidelines according to local and/or institutional standards for management of diabetes mellitus (such as those provided by the American Diabetes Association) during the study
	

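### Table 10.3 lowers the BYL719 dose after resolved grade 3 hyperglycemia with no Cycle 1 exception, against the Cycle 1 reduction ban, so a patient can count as DLT-free at a dose she did not take throughout Cycle 1

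*Combined protocol and SAP*

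**What the plan says.** **Hyperglycemia guidance (Section 10.10.3).** The lead-in states: "Any patient experiencing hyperglycemia will be managed per the guidelines in the table below". For asymptomatic grade 3, Table 10.3 omits BYL719 and then says: "If fasting glucose resolves to Grade 1 within 14 days, then re-start BYL719 and reduce 1 dose level". The table does not mention Cycle 1. Its first bullet adds: "The below are guidelines that may be modified at the discretion of the Principal Investigator".

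**Cycle 1 ban (Section 9.5, repeated in Section 10.10.2).** The rule reads: "Inpatient dose reductions of BYL719 will not be allowed during Cycle 1 (within 28 days of starting study treatment), unless a DLT has occurred". The same sentence requires that this DLT already be in the count. The stated purpose is an accurate determination of the tolerable dose. Section 10.10.2 also says that before Cycle 1 is complete, treatment "can be held for up to 7 days for any reason, and then resumed at the same dose".

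**DLT definition (Section 9.4, Table 9-2).** Confirmed grade 3 hyperglycemia is a DLT if it is one "that does not resolve to grade 0 within 14 consecutive days (after initiation of oral anti-diabetic treatment". Section 9.4 includes events that start in Cycle 1 and are confirmed as DLTs later.

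**Evaluability and replacement.** Section 14.2 makes every patient with at least one dose evaluable for toxicity, apart from replaced early dropouts. Replacement applies only "If a patient discontinues study participation during the first cycle (within 28 days of starting study treatment) for reasons unrelated to an adverse event" (Section 14.2 adds disease progression).

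**The concern.** For the same Cycle 1 patient, one section prescribes a lower dose and two others prescribe the assigned dose. Section 10.10.2 sends the reader to Section 10.10.3 for hyperglycemia, once in its text and once in Table 10-2. However, the ban names no hyperglycemia exception, Table 10.3 does not mention the ban, and neither is given precedence.

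The Cycle 1 DLT count at the assigned dose determines the recommended phase II dose. If Table 10.3 is followed, a patient can enter that count as DLT-free although part of her observation window was spent one level lower. The ban exists to prevent this. In practice the question falls mainly on Arm D, whose recommended dose was set at 350 mg, the top level (Section 4.0). Arm C's expansion was on hold in June 2015.

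**Working it through.** **1. The plan's own figures.** Section 14.2 gives escalation probabilities of .91, .71, .49 and .31 at true DLT risks of .10, .20, .30 and .40. With P = (1−p)³ + 3p(1−p)² × (1−p)³, I obtain .9061, .7086, .4943 and .3093. They reproduce, and no figure in the plan is wrong on this point. The issue is which dose a patient's outcome is credited to.

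**2. The rules side by side**, for confirmed asymptomatic grade 3 hyperglycemia arising in Cycle 1:

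| Course | Table 10.3 | Sections 9.5 and 10.10.2 | Table 9-2 |
|---|---|---|---|
| Grade 1 within 7 days, grade 0 within 14 days of oral treatment | Restart one level lower | Same dose | No DLT |
| Grade 1 within 7 days, not grade 0 by 14 days | Restart one level lower | Same dose until a DLT is counted | DLT, even if confirmed after Cycle 1 |
| Not Grade 1 within 14 days | Discontinue BYL719 | – | DLT |

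Only the first row leaves a patient credited as DLT-free at a dose she did not keep. The row of Table 10.3 also covers symptomatic grade 2, but that may be a DLT as an intolerable grade 2 event, so I leave it aside.

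**3. Timing.** Assume grade 3 at the Day 15 draw, with that day's dose already taken and the hold and oral treatment starting on Day 16. The 14-day clock ends on Day 16 + 14 = Day 30. Table 10.3 itself says that "hyperglycemia usually resolves within a few days after BYL719 omission". After a hold of 3 to 7 days, the restart falls on Days 19 to 23, before the clock ends and within Cycle 1.

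**4. Exposure (illustration only).** Arm D doses fall on Days 1–5, 8–12, 15–19 and 22–26, which is 20 doses. The calendar does not shift for omissions (Table 10-2 notes).

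- 3-day hold (Days 16–18): 11 assigned, 3 omitted, 6 lower (Days 19, 22–26); 6/20 = 30%.
- 4- to 6-day hold: 11 assigned, 4 omitted, 5 lower; 5/20 = 25%.
- 7-day hold (Days 16–22): 11 assigned, 5 omitted, 4 lower (Days 23–26); 4/20 = 20%.
- Draw on Day 12, hold Days 13–15: 9 lower; 9/20 = 45%. Draw on Day 18, hold Days 19–25: 1 lower; 1/20 = 5%.

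In Arm C (14 doses, Day 15 draw), a 3-day hold leaves Days 19–21, so 3 of 14 are lower. A 6- or 7-day hold leaves none.

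These are not bounds. Table 10.3 allows up to 14 days for resolution, and a Day 18 draw with an 8-day hold (Days 19–26) leaves no lower doses in Arm D. Earlier detection through extra glucose checks could give more.

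**5. Effect on the cohort decision.** Section 9.5 accepts a dose with no more than 1 DLT in 6. For one such patient in a cohort of six:

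- One other counted DLT: 1/6 = 16.7% as scored; 1/5 = 20.0% if she is excluded as not evaluable.
- No other DLT: 0/6 as scored; 0/5 if excluded.

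Exclusion adds no DLT. It leaves the cohort one evaluable patient short of six.

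**6. Frequency.** The text available for review gives no Cycle 1 grade 3 rate at 350 mg with exemestane. Single-agent daily dosing gave 4/16 = 25% grade 3/4 at 400 mg and none at 270 mg (Section 10.10.3). Neither matches the Arm D regimen.

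**7. Comparable toxicities.** In Table 10-2, grade 3 anemia, neutropenia, AST/ALT and amylase/lipase, and grade 2 creatinine and bilirubin, lead to a reduction only past the duration that makes the event a DLT. Diarrhea and nausea/vomiting both turn on 48 hours. A first grade 3 rash needs no reduction (Section 10.10.4). Grade 3 hyperglycemia departs from this pattern, which suggests an oversight.

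**The case against.** The strongest reply is that the texts can both be followed. The ban is mandatory, specific to Cycle 1 and stated twice, while Table 10.3 is guidance for all cycles that the Principal Investigator may modify. Keeping the assigned dose in Cycle 1 breaches neither. That stands, and it makes the ban the more likely intended rule. It does not ensure that the ban was applied, because the pointer in Section 10.10.2 leads from the ban to the contrary instruction and could be read as letting Table 10.3 govern.

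Cases are also likely to be few. In Arm D the Day 15 draw follows two drug-free days and in Arm C seven, with a half-life of about 10 hours (Section 3.5.2). That stands too.

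There are safeguards: discussion of held-therapy issues with the drug manufacturer (Table 10-2 notes), calls at least monthly (Section 9.5), the Cycle 2 safety review (Section 9.4), the rule of 4 or more DLTs in an expansion arm (Section 9.6), removal for a violation that makes a patient inevaluable (Section 13.1), and compliance audits at least twice a year (Section 16.2). They could bring a case to light. None says how a non-DLT patient reduced in Cycle 1 counts toward her assigned dose.

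A reader might infer that the protocol has no rule for scoring such a patient at all. That goes too far: Table 9-2 with Sections 9.4 and 14.2 decides DLT or no DLT, and late confirmation is covered. The Principal Investigator also decides DLT status when a repeat glucose falls in a lower grade (Section 10.10.3).

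**Conclusion.** The contradiction is real and minor. It affects only a patient with confirmed grade 3 hyperglycemia who restarts one level lower within Cycle 1 and reaches grade 0 within 14 days of starting oral treatment. She is scored DLT-free at a dose she did not take throughout the window, and the replacement rule does not cover her.

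The bias cannot be sized. The exposure shares (4 to 6 of 20 doses in Arm D for a Day 15 draw) rest on the assumed draw day, hold length and unchanged calendar.

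A reader might infer that one such patient would have overturned the 350 mg recommendation, by counting her as a second DLT (2/6 = 33%). The documents do not support this: under Table 9-2 she has no DLT. Nor do they show that any such patient existed.

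**What to change.** 1. State in Table 10.3, with a cross-reference in Table 10-2, that in Cycle 1 the ban in Sections 9.5 and 10.10.2 governs. Add that if the investigator judges the same dose unsafe, the event is counted as a DLT before the dose is reduced.
2. Accrual closed at 51 patients (Section 1.0), so the wording now mainly records the intended rule. The useful step is to list every dose-finding patient whose dose was reduced in Cycle 1 without a counted DLT: arm, assigned dose, day, reason, and doses taken at the assigned level. If there are any, report the DLT count at that dose level as scored and with those patients excluded as not evaluable. If there are none, say so, and the point is closed.

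The cost is one sentence, one cross-reference, one listing and possibly one small table. Section 9.3 already requires dose changes and interruptions to be recorded. The downside is a little extra analysis and a possibly less favourable DLT rate at the recommended dose.

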10.10.4 Rash Management Guidelines

- BYL719 can be associated with maculopapular rash, as discussed in Section 3.7 above. The below are recommendations that have been developed to guide meticulous management of this toxicity and may be modified at the discretion of the Principal Investigator. Discussion or formal consultation with dermatology is recommended with rash of any grade.

Grade (CTCAE v4.0)	Dose adjustment and management recommendations
Grade 1	
 • Maintain BYL719 dosing. • Augment antihistamine dosing or consider alternate/additional agent(s) (e.g. hydroxyzine 25 mg bid, non-sedating regimen) for at least 28 days • Consider topical corticosteroid preparation bid for affected areas for at least 28 days.
Grade 2	
 • Maintain BYL719 dosing. • Consider augmenting antihistamine dosing or consider alternate/additional agent(s) (e.g. non-sedating regimen during the daytime and sedating at QHS such as hydroxyzine 25 mg AM and noon followed by diphenhydramine 25-50 mg QHS) for at least 28 days. • Consider topical corticosteroid preparation bid for affected areas for at least 28 days. • Oral corticosteroid (recommend prednisone 10mg PO TID for 10 days). If rash resolves to Grade 0-1 within 10 days, oral corticosteroid may be discontinued, tapered dosing not needed. If oral prednisone administered continuously for >10 days, tapered dosing is indicated. Intravenous steroid administration can be substituted for oral administration. • If rash is not grade \leq1 within 14 days of optimal medical management, consider increasing steroid duration, with taper)


Grade 3/intolerable Grade 2
	
 • Hold BYL719 dosing until rash resolved to Grade 0-1 and consider dermatology consult for skin biopsy and photographs. • Initiate antihistamine dosing. Recommend non-sedating regimen during the daytime and sedating at QHS (e.g. hydroxyzine 25 mg AM and noon followed by diphenhydramine 25-50 mg QHS) for at least 28 days. • Topical corticosteroid preparation bid for affected areas for at least 28 days. • Oral corticosteroid (recommend prednisone 10mg PO TID for 10 days). If rash resolves to Grade 0-1 within 10 days (and does not recur with redosing; see below for guideline on rechallenge), oral corticosteroid may be discontinued, tapered dosing not needed. If oral prednisone administered continuously for >10 days, tapered dosing is indicated. Intravenous steroid administration can be substituted for oral administration. • If rash is not grade ≤ 1 in 14 days, continue or readminister oral corticosteroid until resolved and BYL719 is restarted. • A dose reduction of one dose level is recommended if this is a second occurrence. Dose reduction is not necessary following the first occurrence of Gr 3 or intolerable Gr 2 rash. • Upon rechallenge with BYL719 (once rash Grade ≤ 1), continue oral corticosteroid for at least 48 hours. If rash and/or pruritus do not recur in 48 hours, discontinue corticosteroid dosing. Antihistamine regimen should be continued.

Grade 4
	
 • Permanently discontinue BYL719 and consider a dermatology consult. • Treatment of rash should follow guidelines for Grade 3/intolerable Grade 2 rash above with the exception of rechallenge and with any additional measures needed. (BYL719 should be permanently discontinued.)

10.10.5 Pneumonitis Management Guidelines

If the pneumonitis is confirmed to be study drug related (BYL719 + Exemestane or Letrozole), BYL719 must be discontinued as well as the combination drug if the relationship is suspected, regardless of the grade.

As per the new guidance, the table can be summarized as hereafter:

Pneumonitis	Required Investigations	Management of Pneumonitis	Study Treatment Modification
Any Grade	
 Obtain appropriate imaging (e.g. high resolution CT scan) Consider broncho-alveolar lavage (BAL) and biopsy if clinically appropriate Infectious causes of interstitial lung disease should be ruled out 	
 Follow institutional practice for management of pneumonitis (e.g. treatment with high dose corticosteroids; concurrent antibiotic therapy if infectious causes are suspected). Consultation with a pulmonologist is highly recommended 	
 Immediately interrupt both BYL719 and Exemestane or Letrozole for any case of suspected pneumonitis. For all patients with confirmed pneumonitis 
 BYL719 should be permanently discontinued Exemestane or Letrozole should be permanently discontinued if suspected to be etiologically related to the pneumonitis

Additional follow-up for selected toxicities

Management of pneumonitis in patients receiving BYL719

All patients will be routinely asked about and observed for the occurrence of adverse events including new or changed pulmonary symptoms (consistent with lung abnormalities). Patients who are suspected to have developed pneumonitis should suspend study treatment (BYL719 and Exemestane or Letrozole) immediately and undergo appropriate imaging (high resolution CT scan); and broncho-alveolar lavage and biopsy should be considered if clinically appropriate. Infectious causes of interstitial lung disease should be ruled out. Investigators should follow institutional practice for management of pneumonitis which generally includes treatment with high dose corticosteroids; antibiotic therapy should be administered concurrently if infectious causes are suspected. Consultation with a pulmonologist is highly recommended for any pneumonitis case during the study treatment. BYL719 and any other drug (if suspected to be etiologically related to the AE of pneumonitis) should be permanently discontinued in all patients with confirmed pneumonitis.

